1.1.2 Secondary Objectives

1.1.2.1 To examine baseline to 8-week changes in disease-specific quality of life, pain severity, pain-related anxiety, depression, and heart rate variability in patients receiving the ACT intervention.

1.1.2.2 To examine between-group differences in disease-specific quality of life, pain severity, pain-related anxiety, depression, and heart rate variability from baseline to 8 weeks.

1.1.2.3 To examine patterns of change from baseline to 8 weeks to 32 weeks in all primary and secondary outcome measures.

1.1.2.4 To examine potential mediators between pre- and post-treatment pain interference, including pain acceptance, psychological flexibility, as well as cognitive diagnosis (ADHD, LD), disease characteristics (stable vs. progressive disease, location of plexiform neurofibroma), and recent life events to determine whether these variables influence the effectiveness of the intervention.

1.1.2.5 To compare the reliability and validity of the two pain interference measures: the Pain Interference Index (PII) and the PROMIS Pain Interference scale.

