1.2.4 General Overview

The proposed study will use a randomized controlled trial design to compare the treatment group (Acceptance and Commitment Training; ACT) to a wait-list group (WL) in adolescents and young adults ages 16 – 59 years with NF1 and PNs who report chronic pain. Patients will be recruited from [name] NF1 program at the National Cancer Institute, from NF1 clinics around the country, and via the Children's Tumor Foundation (CTF) registry. With all patients, we will implement an 8-week in-person and internet-delivered ACT intervention. All participants will complete their Time 1 assessment (ECG and questionnaires) on day 1 at the NIH before being randomized.

Participants assigned to the ACT group will meet with a trained ACT therapist for two in-person sessions at the NIH (days 1 and 2). Upon returning home, weekly emails will be sent to patients

for 8 weeks, each containing ACT-related information and exercises to complete at home. Video chat sessions will be conducted via computer at weeks 2, 4, and 6. These patients will return to the NIH at week 8 for their Time 2 assessment (repeat ECG and questionnaires). They will be encouraged to continue using ACT techniques in their daily lives. They will be sent follow-up questionnaires to complete electronically from home six months following completion of the 8-week intervention (week 32; Time 3).

Participants assigned to the WL group will return home after completing the Time 1 baseline assessment. They will return to the NIH at week 8 to complete Time 2 follow-up measures (ECG, questionnaires); these data will serve as the primary comparison with the ACT group and will also serve as their baseline assessment for the ACT arm. These participants will then receive the same ACT intervention as described above (two 2-hour in-person sessions, weekly emails, biweekly video chat sessions). They will return to the NIH after the 8-week ACT intervention (at about week 16) to repeat follow-up measures, and will then be encouraged to continue using ACT techniques in their daily lives. Six months later (week 40), they will complete questionnaires online from home. Thus, because they cross over to the ACT intervention after the wait-list period, participants in this group will complete the measures a total of 4 times (as opposed to 3 times in the ACT immediate intervention group).

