At the completion of each visit or set of follow-up questionnaires, participants in both groups will receive a small amount of money (\$30) to thank them for their time. The 8-week data will be the primary endpoint and analyses will be conducted to determine changes over time in ACT versus WL on the primary outcome measure (pain interference) and various secondary measures (outlined below). Forty-one patients per arm will provide 80% power to test the 0 to 8-week differences in changes from baseline between the two arms.

| | Days 1-2 | Weeks 1-8 | Week 8 | Weeks 8-16 | Week 16 | Week 32 | Week 40 |
|-----|--|--|--|--|--|--|--|
| ACT | 
 Time 1 evaluations In-person ACT sessions | 
 Weekly emails Video chat weeks 2,4,6 (home) | 
 Time 2 evaluations (NIH) | 
 Continue ACT practice (home) | | 
 Time 3 questionnaires (home) | |
| WL | 
 Time 1 evaluations | | 
 Time 2 evaluations In-person ACT sessions | 
 Weekly emails Video chat weeks 2,4,6 (home) | 
 Time 3 evaluations (NIH) | 
 Continue ACT practice (home) | 
 Time 4 questionnaires (home) |

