3. Imaging (optional): We will examine prior scans of patients' plexiform tumor *if available*. We will not perform imaging as part of the current study. If patients have a prior scan taken within one year of beginning this study, we will use this to document location of the PN. If two prior scans are available taken approximately 1 – 2 years apart, we will use these to determine if the PN is stable vs. progressive. We will ask patients who have scans from an outside institution to have them mailed to [name], NCI Pediatric Oncology Branch, [name], or [contact].

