3.1.2 Follow-up

Participants in both groups will return to the NIH at the end of the 8-week intervention (not to exceed 12 weeks after their initial NIH visit). During this visit, all participants will repeat the baseline evaluations: they will complete follow-up questionnaires as listed in section [2.4](#) and will have a second ECG. After those evaluations, the ACT participants will return home with instructions to continue using the ACT techniques in their daily lives. The WL participants will then receive the 2-session in-person ACT intervention (typically over two days), and then will return home to take part in the weekly emails and individual video chat sessions.

At the end of their 8-week intervention, participants in the WL group will return to the NIH for their final in-person visit when they will complete the follow-up questionnaires again and will receive their final ECG. If it is a hardship for patients in the WL group to return for a third visit (i.e., for those who live across the country), they will be given the option to complete the questionnaires online from home. Thus, we will have questionnaire data for these patients but will forego their second follow-up ECG data.

Both groups will complete a final set of questionnaires from their home computer, tablet, or smartphone about six months (about 24 weeks) after the formal intervention ends.

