6 STATISTICAL SECTION

6.1 PRIMARY AND SECONDARY OUTCOMES

The primary objective of the trial is to compare pain interference mean score changes from baseline to 8 weeks between the ACT intervention group and the WL group. In the pilot study conducted by our group, mean scores on PII self-report went from 2.1 (1.0) to 1.5 (1.1), with paired differences having a mean change of -0.68 and SD=1.3. Based on this preliminary estimated change for the ACT group, and an assumption of no change in the WL group and a corresponding, reduced SD = 0.8, forty-one patients will be needed per group to have 80% power to detect a difference in change score between the two arms of -0.68, using a t-test with significance level of .05 (two-sided). Secondary analyses will be performed to compare between-group changes from baseline to 8 weeks and from baseline to 32 weeks on the following endpoints: disease-related quality of life, pain severity, pain-related anxiety, and depression. Given the wide age range of the study, we will stratify analyses by age (16 – 24 years; 25 – 59 years). Descriptive statistics will be computed on the primary and secondary outcome measures (means, standard deviations, etc.). If there are significant differences between the groups at baseline (for example, with respect to gender or number of patients on pain medication), analysis of covariance (ANCOVA) may be used to control for these differences statistically during follow-up analyses (treating baseline as a covariate). We also will assess for differences between the group randomized to ACT and the WL group on primary and secondary outcomes, particularly comparing primary results from 0 to 8 weeks for ACT vs. 8 to 16 weeks for WL (receiving ACT starting at 8 weeks); if the results are similar (for example, $p>0.30$ approximately), we will combine these groups to report the overall effect of ACT for 8 weeks, and also examine changes from baseline to 8 weeks and 8 to 16 weeks using an appropriate statistical test. Finally, based on a priori hypotheses and prior literature, we will test for indirect effects of acceptance and psychological flexibility with simple mediation model analyses. We will generate 5,000 bootstrapped samples using Preacher and Hayes' (Preacher & Hayes, 2004) INDIRECT macro. Post-treatment scores will be used for these analyses. Additionally, we will examine whether a previous cognitive diagnosis (ADHD or learning disability), reading ability, disease characteristics (stable vs. progressive disease, location of plexiform neurofibroma), or recent life events, relate to changes over time in the primary outcome with an ANOVA, and if so

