
we may control for these variables in other analyses with an ANCOVA. Finally, we will compare the psychometric properties of the PII and PROMIS Pain Interference Scale by examining internal consistency in the patient sample (computed by Pearson correlations) and the response to change (as described in the primary objective analysis above). Data will be entered into a secure database, then analyzed using SAS statistical software.

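### Section 6.1 names no arm-by-factor term, so its ANOVA of the baseline factors cannot show which of them change the ACT-versus-wait-list effect, as objective 1.1.2.4 asks.

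*Combined protocol and SAP*

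**What the plan says.** Objective 1.1.2.4 (section 1.1.2) lists pain acceptance and psychological flexibility together with cognitive diagnosis, disease characteristics and recent life events. It calls them all potential mediators standing between pain interference before and after treatment, and gives the purpose as "to determine whether these variables influence the effectiveness of the intervention".

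Section 6.1 splits the list.

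- **Baseline factors.** For cognitive diagnosis, reading ability, disease characteristics and life events, the plan will examine whether they "relate to changes over time in the primary outcome with an ANOVA". If they do, "we may control for these variables in other analyses with an ANCOVA". No arm term, arm-by-factor term or analysis set is named.
- **Process variables.** For acceptance and flexibility, the plan states a simple mediation analysis with 5,000 bootstrap samples, and says "Post-treatment scores will be used for these analyses". Section 6.1 names neither the predictor nor any baseline covariate.

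Section 3.3.3 ties statistical control for reading ability to whether people with different reading skills respond differently to the intervention. On timing, section 1.2.4 says the wait-list week-8 data are the primary comparison with ACT and "will also serve as their baseline assessment for the ACT arm". Wait-list patients' own post-ACT visit is at about week 16.

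**The concern.** In a two-arm trial, a factor influences the effectiveness of ACT if the ACT-minus-wait-list difference varies across its levels. That is an arm-by-factor interaction. A factor can relate to change for another reason: patients with progressive disease, for example, might do worse in both arms alike. Adjusting for such a factor afterwards does not show whether it modifies the effect. Without the interaction, a positive ANOVA may reflect prognosis alone, and a null one may hide a factor whose effects differ in direction between arms.

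The baseline factors are also misnamed. They are pre-treatment traits, so they are candidate moderators, not mediators.

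The mediation raises a smaller issue. The objective reads as if pre-treatment pain interference were the predictor, whereas section 6.1 speaks of indirect effects estimated from post-treatment scores, which fits arm as the predictor. Using post-treatment scores alone also leaves the baseline correlation between mediator and pain interference uncontrolled.

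**Working it through.** **Inputs from section 6.1.** Mean change -0.68 (SD 1.3) in ACT and 0 (SD 0.8) in wait-list; 41 per group; two-sided 0.05; 80% power. Section 6.2 allows up to 90 patients, or 45 per arm if allocation is 1:1 (assumed). The documents give no factor prevalences or effects, so those below are assumed.

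**The plan's own figure.** The root-mean-square SD is sqrt((1.3² + 0.8²)/2) = 1.079. The normal approximation gives 40 per group. The noncentral t gives 41, with power 80.5%. The stated 41 reproduces.

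**A purely prognostic factor: 0.6 points in both arms, 50/50 split, 82 patients.**

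- Factor-only ANOVA: the variance within factor levels is the mean within-arm variance plus the between-arm part, 1.165 + 0.34² = 1.281. SE = sqrt(1.281 × 4/82) = 0.250. Power ≈ Φ(0.6/0.250 - 1.96) = 67%. Simulation gives 66% to 67%.
- Adding arm as a main effect: SE = sqrt(1.165 × 4/82) = 0.238, power ≈ 71% (70% by simulation).
- Interaction test: 5% by simulation, as it should be, since nothing is modified.

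**True moderators, simulated, 50/50 split.**

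| Factor effect (ACT / wait-list) | Factor-only ANOVA | Interaction test, no baseline PII |
|---|---|---|
| +1.36 / 0 | 74% | 79% |
| +0.68 / 0 | 25% | 29% |
| +0.68 / -0.68 | 3% to 4% | 79% to 80% |

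**What the interaction test can deliver.** SE = sqrt((1.3² + 0.8²)/n × (1/p + 1/(1-p))), with n per arm and p the prevalence. At n = 41 and p = 0.5 this is sqrt(2.33/41 × 4) = 0.477. The smallest interaction detectable with 80% power is 2.80 × 0.477 = 1.34 points. Power for 0.68 is Φ(0.68/0.477 - 1.96) = 30%. At p = 0.2 the SE is 0.596, the detectable interaction 1.67 and power for 0.68 is 21%. An interaction of 0.68 would need about 159 (p = 0.5) to 248 (p = 0.2) per arm for 80% power.

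With baseline PII in the model, power for 0.68 is 24% to 39% over 41 to 45 per arm and 20% to 50% prevalence, with a 95% CI half-width of about 0.8 to 1.1 points. This takes the ACT pre-post correlation as (1.0² + 1.1² - 1.3²)/(2 × 1.0 × 1.1) = 0.24 from the pilot SDs. The wait-list correlation is 1 - 0.8²/2 = 0.68, assuming unit SDs. The pilot value is itself an assumption: the pilot means differ by 0.6 (2.1 to 1.5) while the paired change is 0.68, so the SDs may come from different sets of patients.

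**Disease status.** Section 2.4 classifies stable versus progressive disease only "If two prior scans are available taken approximately 1 – 2 years apart". If that leaves 25 per arm (assumed), power for 0.68 is 16% to 23% and the half-width about 1.1 to 1.4 points.

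**Mediation.** This simulation takes arm as predictor, week-8 scores in both arms and no true mediator-to-PII path. It assumes five combinations of baseline correlation (-0.3 to -0.6) and pre-post correlation (0.5 to 0.7). Post-treatment scores alone give a false indirect effect in 8% to 67% of trials. Adding both baselines gives 5% to 7%, but only if the week-8 residuals of mediator and PII are uncorrelated. At residual correlation -0.2 the adjusted rate is 40% to 44% (unadjusted 49% to 83%). At -0.3 it is 71% to 76% (unadjusted 68% to 85%), so adjustment no longer helps reliably.

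**The case against.** Section 1.2.4 speaks of "changes over time in ACT versus WL on the primary outcome measure", so a group-by-time-by-factor ANOVA may be what the authors intend. That is possible, but the phrase describes the primary and secondary comparisons, and section 6.1 does not carry it over to the factors. The age-stratified analyses do not fill the gap either: age is not among the 1.1.2.4 factors, and no interaction test is stated.

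The crossover case is extreme, since it needs an opposite effect in untreated patients. For a factor acting only within ACT, the ANOVA detects almost as often as the interaction test. This stands. The case therefore rests on failure to separate prognosis from moderation, not on lost detection.

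The interaction test is weak at this sample size. This also stands. It is a reason for an exploratory label and confidence intervals, not for keeping a test of a different question.

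Two stronger readings are tempting. A reader might infer that nothing in section 6.1 addresses objective 1.1.2.4. It does: a mediation analysis is stated for acceptance and flexibility. A reader might also infer that the mediation has no time point. It has one, post-treatment. Section 1.1.1.1 equates week 8 with the end of the intervention, and section 1.2.4 makes week 8 the primary endpoint. Only the wait-list visit is not explicit, and week 8 is the better-supported reading. If wait-list week-16 scores were used, both arms would have had ACT and arm would carry no contrast. That follows by construction, and nothing in the plan shows it is intended.

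**Conclusion.** The point holds for the baseline factors in objective 1.1.2.4, and for reading ability, whose use section 3.3.3 ties to differential response. As written, the ANOVA would flag a purely prognostic 0.6-point factor in about two thirds of trials, and the result could not be told from moderation. That figure rests on the plan's SDs and arm effect, and on an assumed effect and 50% prevalence. At 30% and 20% prevalence it is 58% and 47%. Only two-level factors were examined; tumour location and the 43-item life-events list have no stated coding. Section 6.1 does not itself claim that a positive ANOVA shows moderation, so the defect is a missing analysis and not a false statement.

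The mediation point is secondary: the predictor needs reconciling between the objective and section 6.1, the wait-list visit needs naming, and baseline covariates are absent. Its error rates depend wholly on assumed correlations.

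The primary test and sample size are unaffected. The change should be made because it is nearly free and the objective is otherwise unanswered for these factors.

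**What to change.** **Baseline factors.** For each factor in 1.1.2.4 and for reading ability, model baseline-to-week-8 PII change on baseline PII, arm, factor and arm-by-factor. Report the interaction with its 95% CI and the number analysed. Call these factors moderators in 1.1.2.4, and label the results exploratory. State that with power of about 20% to 39% for a 0.68-point interaction, a null result is not evidence of no moderation.

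**Mediation.** State arm as the predictor, take week-8 mediator and PII scores in both arms, and include baseline PII and the baseline mediator as covariates. Label it exploratory. Both measures come from the same visit, at which "all participants will repeat the baseline evaluations", so also state that adjustment does not remove same-visit residual correlation or establish time order.

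**Cost.** Wording in 1.1.2.4 and 6.1. No new data, visits or patients.

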3.3 QUESTIONNAIRES

3.3.1 Patient Questionnaires

3.3.1.1 Pain Interference

The Pain Interference Index (PII) is a 6-item questionnaire meant to assess the degree to which pain has interfered with daily activities in the past week ([Appendix C](#)). This measure initially was developed and validated in Sweden with youth with longstanding idiopathic pain (Wicksell, Melin, Lekander, & Olsson, 2009b). In collaboration with the Swedish researchers, the authors of the current study translated the measure to English and also created a parallel parent report version (PII-P) and an adult self-report version. The youth self-report PII has been validated in patients ages 6 to 25 years with NF1 and other chronic illnesses (Martin et al., 2014). For this study, this version will be administered to patients ages 16 to 17 and to 18-25 year olds who are still in school. The adult self-report version is parallel to the youth self-report version, with minor wording modifications made (changing “school” to “work”). Initial reliability and validity data of the adult self-report version are positive ($\alpha = .94$; manuscript in preparation). Both versions of the scale take about 2 minutes to complete.

The PROMIS Pain Interference scales will be administered as another assessment of pain interference (Appendices C and D); (Amtmann et al., 2010; Varni et al., 2014). The adult 8-item short form will be administered to participants ages 18 - 59, and the pediatric 8-item short-form will be given to participants ages 16 and 17 years. Both of these scales ask the respondent to consider how much pain has interfered with things like sleep, mood, and leisure activities, in the past week. Items are formatted on 0-4 Likert scales. These measures each take about 2 minutes to complete. The PII and the PROMIS pain interference scales are both being given since they each have advantages and disadvantages. Specifically, the PII’s limited items may not capture all relevant aspects of pain interference in NF1, but this measure has strong preliminary reliability and validity data in this population, which the PROMIS does not yet have. Moreover, giving both measures in conjunction is the current recommendation of the Patient-Reported Outcomes (PRO) working group of the Response Evaluation in Neurofibromatosis and Schwannomatosis (REiNS) collaboration.

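### Applying the primary analysis to the PII and to PROMIS separately gives two treatment effects but no estimate of how their responsiveness differs

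*Combined protocol and SAP*

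**What the plan says.** Secondary objective 1.1.2.5 is "To compare the reliability and validity of the two pain interference measures", the PII and PROMIS. Section 6.1 carries it out in one sentence: "we will compare the psychometric properties of the PII and PROMIS Pain Interference Scale", by looking at internal consistency and at "the response to change (as described in the primary objective analysis above".

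The analysis referred to is set out at the start of Section 6.1. Its aim is to "compare pain interference mean score changes from baseline to 8 weeks between the ACT intervention group and the WL group". The sample size is justified "using a t-test with significance level of .05 (two-sided", with "80% power to detect a difference in change score between the two arms of -0.68".

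The two scales are scored differently. The PII has six items rated 0 to 6 (Appendix C), and eligibility uses their mean (Section 2.1.1.4). PROMIS has eight items, and Section 3.3.1.1 says of it "Items are formatted on 0-4 Likert scales". Participants aged 18 to 59 receive the adult PROMIS form and those aged 16 and 17 the pediatric form.

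I found no standardised responsiveness index, no contrast between the scales, no interval for such a contrast and no rule for scoring or combining the two PROMIS forms.

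**The concern.** The primary analysis compares arms within one scale. Responsiveness asks a different question: for the same patients and the same treatment contrast, does one scale register more change relative to its noise than the other? Running the within-scale analysis twice answers the treatment question twice and leaves the between-scale question without an estimate.

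Two features make this more than a matter of presentation. The raw effects are in different units, so their sizes cannot be compared directly. The two results also come from the same patients and are therefore correlated, and two separate tests make no use of that. At stake is the responsiveness part of objective 1.1.2.5: a reader given two effects and two p-values may draw a conclusion that the data do not support.

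**Working it through.** **Inputs from Section 6.1.** For ACT, "paired differences having a mean change of -0.68 and SD=1.3". For the wait-list arm, no change and SD 0.8. There are 41 patients per arm and a two-sided 0.05 t-test.

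**Step 1: reproduce the plan's figure.** Pooled SD of change = √[(1.3² + 0.8²)/2] = √1.165 = 1.079. Standardised effect = 0.68/1.079 = 0.63. (The Précis calls this .68 standard deviation; Section 6.1's own SDs give 0.63, which I use.) The normal approximation gives 40 per arm. The noncentral t gives power of 79.5% at 40 and 80.5% at 41 (80.3% with Welch degrees of freedom). The stated 41 reproduces and is not in dispute.

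**Step 2: units.** Multiplying a scale by a constant multiplies the raw effect and its standard error equally. With an arbitrary factor of 5, −0.68 becomes −3.40 and the t statistic does not move. Raw effects therefore cannot be compared across scales, whereas t statistics and standardised effects can.

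**Step 3: disagreement between tests when responsiveness is identical.** Give both scales the effect 0.63. The noncentrality is 0.68/√[(1.69 + 0.64)/41] = 2.85, and the normal-approximation power is 0.81 per scale. P(exactly one significant) = 2 × [power − P(both significant)], from a bivariate normal. A simulation (20,000 trials, 41 per arm, t-test on each scale) checks this and also gives the spread of the paired difference in standardised effects. The correlation is assumed: it applies to the test statistics in the formula and to the change scores in the simulation.

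| Assumed correlation | Exactly one significant, formula | Exactly one significant, simulation | SD of difference in standardised effects | 95% half-width (1.96 × SD) |
|---|---|---|---|---|
| 0.5 | 21.5% | 22.5% | 0.235 | 0.46 |
| 0.6 | 19.2% | 20.2% | 0.212 | 0.42 |
| 0.7 | 16.6% | 17.2% | 0.183 | 0.36 |
| 0.8 | 13.6% | 14.2% | 0.150 | 0.29 |
| 0.9 | 9.6% | 9.8% | 0.107 | 0.21 |

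**Step 4: the opposite error.** Let PROMIS be about two-thirds (0.67) as responsive, a true gap of about 0.63 × 0.33 = 0.21. Both tests are still significant in 43%, 45% and 47% of simulated trials at correlations 0.5, 0.7 and 0.9. Agreement on significance therefore does not show equal responsiveness.

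**Step 5: what a direct comparison could do.** For that same gap of 0.21, a paired 95% CI would exclude zero in about 15%, 21% and 50% of trials at correlations 0.5, 0.7 and 0.9. The direct contrast answers the right question, but with modest precision.

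**The case against.** The strongest reply has three parts.

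First, a reader might infer that significance is the only thing the two analyses have in common. The documents do not support that. A t statistic has no units, and Section 6.1 plans means and SDs for the primary and secondary outcome measures. PROMIS is not named there, but if its means and SDs are reported, standardised effects follow at once. This stands. What is missing is a prespecified contrast with its uncertainty, not every comparable quantity.

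Second, a reader might infer that the plan will rank the scales by which one reaches significance, and so take 10% to 22% as a rate of wrong rankings. No such rule is written. Section 6.1 speaks only of examining response to change, and its reference back may point to the quantity and the time window and not to the t-test, which appears in the sample-size sentence. This also stands: the percentages are rates of discordant tests. On either reading, however, the plan contains no between-scale estimate.

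Third, little depends on the result. Section 3.3.1.1 says each scale has advantages and disadvantages and that giving both follows a working group's recommendation. That limits the priority, but the comparison remains a declared objective.

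**Conclusion.** The point holds in a limited form. The one method named for comparing response to change yields a treatment effect and a test for each scale, but neither an estimate of the difference in responsiveness nor an interval for it. That part of objective 1.1.2.5 is left unanswered.

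Taking the two p-values as the comparison would be unsafe. Equally responsive scales would disagree on significance in about 10% to 22% of trials, and a scale one-third less responsive would still be significant together with the other in 43% to 47%. These figures rest on Section 6.1's effect and SDs, 41 per arm, an assumed correlation of 0.5 to 0.9, and PROMIS change having the same ratio of SDs between arms as the PII. The documents supply no PROMIS SD and no correlation.

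The primary endpoint, the sample size and the treatment conclusion are untouched.

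**What to change.** Replace the reference back to the primary analysis with a paired contrast, for example:

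> In patients with both scales at baseline and week 8, we will compute for each scale the between-arm difference in 0–8 week change divided by the pooled SD of change. We will report the PII-minus-PROMIS difference in these standardised effects with a 95% CI from 5,000 bootstrap samples of patients drawn within arm, keeping each patient's two scores together. The analysis will be done in participants aged 18–59, who complete the adult PROMIS form. The result will be reported as an estimate; one test being significant and the other not will not be taken as evidence that one scale is more responsive.

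If ages 16 and 17 are to be kept, standardise PROMIS change within form before pooling and treat the PII the same way. A single PROMIS SD across two different forms is not defined as the plan stands. State the PROMIS scoring rule in either case.

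The cost is a few sentences in Section 6.1 and a short SAS program on data already collected; 5,000 bootstrap samples are already planned for the mediation analysis. The drawback is precision. The half-width of about 0.2 to 0.5 SD assumes 41 per arm with both scales, and it widens if the analysis is restricted to adults or if patients lack week 8 data.
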